11.4.2. Treatment of ties

In case of ties (i.e. more than one case at the same time, very unlikely with such a small incidence), the Breslow method will be used.

11.4.3. Covariates

The Cox regression methodology can take into account specific risk factors which might have been imbalanced, by chance, at the beginning of the trial between the vaccinated and control group.

As a secondary analysis, ATP analyses evaluating first or only episodes of first case definition will also be performed adjusting for other covariates. Covariates are:

- Country
- Gender
- Diabetes at screening
- Year of occurrence (time-dependent covariable, treated differently)
- Age: $\leq 25, > 25$
- The variable indicating whether a subject was vaccinated with BCG and/or has a BCG scar
- Smoking: currently smoker or not

Please find in the below table how the variable indicating whether a subject was vaccinated with BCG and/or has a BCG scar is defined based on data coming from the CRF

CRF categories for BCG history (previous BCG vaccination)	CRF categories for presence of a BCG vaccination scar	The covariate= subject was vaccinated with BCG and/or has a BCG scar
Yes	Yes	Yes
Yes	No	Yes
Yes	Not done	Yes
No	Yes	Yes
No	No	No
No	Not done	Unknown
Unknown	Yes	Yes
Unknown	No	Unknown
Unknown	Not done	Unknown

Please find in the below table how the current smoker is defined based on data coming from the CRF

Categories for smoking history in the CRF	Current smoker
Yes, currently smoking cigarettes every day	Yes
Yes, currently smoking cigarettes some days	Yes
No, currently not but previously regularly	No
No, currently not but never regularly	No

The VE will be given at each level of each of these covariates, like for a subgroup analysis. A forest plot will be given representing these VE and their 90% CI. This is really exploratory and requires caution in interpretation due to the low number of cases.

Due to the low number of cases, the decision to adjust for all the covariates all together or in a univariate way will be taken based on the outcome of the model fit (if standard deviation is too high, or coefficient is infinity or the model did not converge, then the adjustment will be univariate, covariate by covariate separately, [Harrell1984], [Harrell1996], [Peduzzi1996] Subjects with missing values for the covariates taken into account into the model will be not considered into the model.

For the year of occurrence, as it is a time-dependent covariate, this will be analysed through the piecewise Cox model.

```
proc phreg data=TB OUTEST=oo COVOUT;;
model fu_year*event(0)=treatt1 treatt2;
treatt1 = GROUP * (fu_year LE 1.5);
treatt2 = GROUP * (1.5 < fu_year );
run;
```

The hazard ratio and VE with the CI will be computed inside each interval. The 90% CI for the hazard ratio linked to the i interval is equal to $\exp(\text{estimate of the coefficient for the } i\text{ interval} \pm 1.645 * \text{standard error for the estimator of the coefficient for the } i\text{ interval})$

11.4.4. Check of the assumption of the proportional hazards under the Cox regression

Cox regression assumes proportional hazards throughout the follow-up period. This assumption will be checked by including a time-varying covariate, an interaction between the treatment and the time-to-event. This can be done easily within proc phreg. If the interaction term between time and group is significant, the null hypothesis of proportionality is rejected.

Time Dependent Cox model

```
proc phreg data=TB_effic;
model fu_year*event(0)=GROUP treatt;
treatt=group*log(fu_year+1);    /*+1 is useful to avoid problems at
time=0;
run;
```

If this assumption of proportion hazards is not respected,

We will further investigate other methods to investigate the variability of the VE over time using a more flexible time-dependent Cox model where we split the time into few intervals and we estimate the hazard ratio within each interval (piecewise Cox model). The problem of the piecewise Cox model is that results will depend on the chosen intervals. In our case, the follow-up time could be split into two periods due to the small number of cases, for example as following.

```
proc phreg data=TB OUTEST=oo COVOUT;;  
model fu_year*event(0)=treatt1 treatt2;  
treatt1 = GROUP * (fu_year LE 1.5);  
treatt2 = GROUP * (1.5 < fu_year );  
run;
```

The split will be decided based on the distribution of the cases over the study time later on following this rule: It will be the time where half of the events has been observed

The hazard ratio and VE with the CI will be computed inside each interval. The 90% CI for the hazard ratio linked to the i° interval is equal to $\exp(\text{estimate of the coefficient for the } i^{\circ} \text{ interval} \pm 1.645 * \text{standard error for the estimator of the coefficient for the } i^{\circ} \text{ interval})$

11.4.5. Methods for Confidence Intervals (CIs) for Vaccine Efficacy based on Cox regression

The CI for VE can then be derived from the Wald CI from Hazard Ratio. This method is implemented in the PHREG procedure of the SAS/STAT package (SAS V9.2).

11.5. Details on case definition 1

For subjects falling into case definition 1, the GeneXpert result (positive, negative/missing) will be cross tabulated with the culture result inside the 2 vaccine groups only for the end of study analysis.

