2. INTRODUCTION

- Study TUBERCULOSIS-018 is an efficacy study with a follow-up of 3 years. The triggered primary analysis will be conducted when all subjects have completed their Month 24 visit.
- In order to preserve the blinding of the study, the triggered primary analysis will be performed by statisticians external to the GSK-AERAS clinical teams and any of the investigator teams.

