3. STUDY OBJECTIVES

3.1. Primary objective

- To evaluate the protective efficacy of two doses of the M72/AS01_E candidate vaccine against **Definite pulmonary TB disease** not associated with HIV-infection, meeting the first case definition, as compared to placebo.

Success criterion to be used for the primary objective:

The lower limit (LL) of the 90% two-sided confidence interval (CI) for the vaccine efficacy (VE) (using a Cox regression model) against first occurrence of Definite pulmonary TB disease not associated with HIV-infection, meeting the first case definition, is above 0%

Refer to Section 4.1 for the definition of the primary endpoint and Section 5 for case definitions.

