3.2. Secondary objectives

Efficacy:

- To evaluate the protective efficacy of two doses of the M72/AS01_E candidate vaccine against **Definite Xpert MTB/Rif positive pulmonary TB disease** not associated with HIV-infection, meeting the second case definition, as compared to placebo.

If the primary objective is met, this secondary objective will be analysed using the following success criterion:

The LL of the 90% two-sided CI for the VE (using a Cox regression model) against first occurrence of Definite pulmonary TB disease not associated with HIV-infection, meeting the second case definition, is above 0%.

- To evaluate the protective efficacy of two doses of the M72/AS01_E candidate vaccine against **Definite pulmonary TB disease** not associated with HIV-infection, meeting the third case definition, as compared to placebo.
- To evaluate the protective efficacy of two doses of the M72/AS01_E candidate vaccine against **Microbiological pulmonary TB disease** meeting the fourth case definition, as compared to placebo.
- To evaluate the protective efficacy of two doses of the M72/AS01_E candidate vaccine against **Clinical TB disease** meeting the fifth case definition, as compared to placebo.

Safety:

- To assess the safety and reactogenicity of two doses of the M72/AS01_E candidate vaccine.

Immunogenicity:

- To assess the immunogenicity of two doses of the M72/AS01_E candidate vaccine.

Refer to Section 4.2 for the definition of the secondary endpoints and Section 5 for case definitions.

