5. CASE DEFINITIONS

First case definition – Definite pulmonary TB, not associated with HIV-infection

- A subject with clinical suspicion* of pulmonary TB disease, with *Mycobacterium tuberculosis* (Mtb) complex identified from a sputum specimen, taken before initiation of TB treatment, by Xpert MTB/RIF and/or microbiological culture and confirmed HIV-negative at the time of TB diagnosis.

Second case definition –Definite Xpert MTB/Rif positive pulmonary TB, not associated with HIV-infection

- A subject with clinical suspicion* of pulmonary TB disease, with Mtb complex identified from a sputum specimen, taken before initiation of TB treatment, by Xpert MTB/RIF and confirmed HIV-negative at the time of TB diagnosis.

Third case definition – Definite pulmonary TB, not associated with HIV-infection

- A subject with clinical suspicion* of pulmonary TB disease, with Mtb complex identified from a sputum specimen, taken up to four weeks after initiation of TB treatment, by Xpert MTB/RIF and/or microbiological culture and confirmed HIV-negative at the time of TB diagnosis.

Fourth case definition – Microbiological pulmonary TB

- A subject with clinical suspicion* of pulmonary TB disease, with Mtb complex identified from a sputum specimen, taken up to four weeks after initiation of TB treatment, by Xpert MTB/RIF and/or microbiological culture.

*Clinical suspicion of pulmonary TB is defined as a subject presenting with one or more of the following symptoms: unexplained cough > 2 weeks, unexplained fever > 1 week, night sweats, unintentional weight loss, pleuritic chest pains, haemoptysis, fatigue or shortness of breath on exertion.

Fifth case definition – Clinical TB

- A subject for whom a clinician has diagnosed TB disease and has decided to treat the patient with TB treatment. Note: for the purpose of the analysis the site PI is considered the clinician providing definite diagnosis.

Case Definition	Localisation	Culture Result	GeneXpert MTB/Rif	HIV status	Other
1st Case Def. Primary Objective*	Pulmonary	Either or both positive for at least one of the 3 sputum		Negative	Sample before TB treatment start
2nd Case Def.	Pulmonary	Any	Positive	Negative	
3rd Case Def.	Pulmonary	Either or both positive for at least one of the 3 sputum		Negative	Sample up to 4 week after TB treatment start
4th Case Def.	Pulmonary	Either or both positive for at least one of the 3 sputum		Negative or positive or unknown or not tested	

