9. PLANNING OF ACTIVITIES

Timeframe	Activities
FSFV	August 2014
During the study	Several analyses for IDMC, especially before last subject last dose 2
Before datalock point	Clean ATP efficacy

Before datalock point, a first check of the elimination codes to be assigned to subjects for the ATP cohort for efficacy (and safety) will be organised (draft Pre-Analysis Meeting PAM). After all subjects have completed 24 months of follow-up, the final PAM for the primary analysis will be organised.

Timeframe	Activities
Every 2 months	Case review
2-3 times/year	IDMC
When 18 primary TB cases are accrued	Weekly case review
From 21 primary TB cases are accrued until all subjects complete their M24 visit	Continuous review of the entire database by the data management and preparation of the triggered primary analysis
When all subjects have completed 24 months of follow-up	All analyses will be performed by an external statistician: efficacy analysis + IDMC + Analysis of safety with masking of single events
Month 36 (study completion)	All analyses

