*Should be with very small frequency due to the lapse of time (6 weeks) considered between database lock point and database freeze

**Data lock point = last subject M24 visit date

Note: In this table, only lab confirmation or not of the TB suspicion is considered, but there are other elements involved in the case definitions, elements which differ from case definition to case definition (ex: HIV status at time of TB diagnosis or timing of sputum sample with respect to TB treatment start). Therefor the censoring occurs for the non-cases at the date when last subject month 24 visit is completed (database lock point), or Month 36 visit or last contact date or date of suspicion if lab data is pending or date of positive lab result if not satisfying the considered case definition whichever comes first.

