11.4. Efficacy

11.4.1. Analysis

VE will be estimated from a Cox proportional hazard regression model (VE=1-hazard ratio) and 90% CIs and Wald p-value will be derived. The primary analysis will be unadjusted but secondary analyses will evaluate the effect of potential covariates.

At the case-driven analysis of efficacy (primary analysis), the success criterion for the primary objective is the following:

The LL of the 90% two-sided CI for the VE (using a Cox regression model) against first occurrence of Definite pulmonary TB disease not associated with HIV-infection, meeting the first case definition, is above 0%.

Kaplan-Meier survival curves for the vaccine and control groups will be presented together with p-values from the logrank test.

If the primary objective is met, the confirmatory secondary objective will be evaluated with the following success criterion:

The LL of the 90% two-sided CI for the VE (using a Cox regression model) against first occurrence of Definite pulmonary TB disease not associated with HIV-infection, meeting the second case definition, is above 0%.

For all other secondary efficacy objectives, Kaplan-Meier survival curves will be plotted and compared by means of the logrank test. The magnitude of the vaccine efficacy will be estimated using Cox regression.

For the primary case definition, the number and proportion of cases will be given by vaccine group and by the number of doses received (1 or 2).

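### If the vaccine arm has no cases, the Wald limit behind both confirmatory success criteria does not exist, and no rule links the SAP's planned exact interval to those criteria

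*SAP*

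**What the plan says.** SAP 3.1 sets the primary criterion on "The lower limit (LL) of the 90% two-sided confidence interval (CI) for the vaccine efficacy (VE) (using a Cox regression model) against first occurrence" of first-definition TB, with 0% as the bound. SAP 3.2 applies the same kind of limit to the second definition: "If the primary objective is met, this secondary objective will be analysed using the following success criterion". Protocol 2.1, 2.2 and 11.7 use the same Cox wording.

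SAP 11.4.1 states: "VE will be estimated from a Cox proportional hazard regression model (VE=1-hazard ratio) and 90% CIs and Wald p-value will be derived". Neither criterion names the type of interval. SAP 11.4.5 does, and it names one type only: "The CI for VE can then be derived from the Wald CI from Hazard Ratio".

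Related provisions exist elsewhere in the SAP:

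- 11.4.3 anticipates an infinite coefficient or non-convergence, but only for the covariate-adjusted model.
- 13.2.3 anticipates all events falling in one arm, but only as a blinding rule for covariate levels.
- 11.8.2 and Section 16 plan a conditional exact CI for each case definition. They sit under the sensitivity-analysis heading, and the title of 11.8.2 presents the method as a replacement for Cox regression.
- 13.3 makes everything outside the two confirmatory tests descriptive.

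On timing, "The triggered primary analysis will be conducted when all subjects have completed their Month 24 visit", and the Table 4 footnote in 10.2 adds "Data lock point = last subject M24 visit date". The case count at the primary analysis is therefore not fixed at 21.

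**The concern.** A Wald limit needs a finite log hazard ratio and standard error. With no vaccine-arm cases the partial likelihood keeps rising as the coefficient goes to minus infinity, so neither exists and whatever the software prints depends on where it stops iterating. The rule would then give success at 1 v 20 and no answer at 0 v 21, which is stronger evidence for the vaccine.

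The formal success call would be lost in the most favourable outcome, or the deciding interval would be chosen after the data were seen. An unevaluable primary also blocks the secondary, which is tested only if the primary is met. Second-definition cases must be identified from sputum "taken before initiation of TB treatment, by Xpert MTB/RIF and confirmed HIV-negative at the time of TB diagnosis", so they are a subset of first-definition cases. Zero on the primary implies zero on the secondary, and the secondary can be zero when the primary is not.

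**Working it through.** **Inputs.** Protocol 11.3: VE 70% (hazard ratio 0.3), 80% power, two-sided 10% level, 21 cases, control attack rate 0.55% per year, 15% loss over 2 years, 3506 subjects (1753 per arm). Assumed because the documents give no figure: 10 to 18 second-definition cases, and a vaccine-to-control follow-up ratio r of 0.95 to 1.05.

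**The plan's own figure.** Freedman's logrank formula gives (1.645 + 0.842)² × (1.3/0.7)² = 21.3 events, against 21 stated. Then 2 × 21.32 / (0.011 + 0.0033) / 0.85 is about 3509 subjects, against 3506. Both are reproduced.

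**Wald behaviour.** For 1 v 20 with equal follow-up, ln(1/20) = −3.00 and SE = √(1 + 1/20) = 1.02. The upper hazard ratio limit is exp(−3.00 + 1.645 × 1.02), about 0.27, so the VE lower limit is 73% and the criterion is met. A Cox fit (Breslow ties, 1753 per arm) gives the same values. For 0 v 21 the iterations give:

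| Iteration | log HR | SE |
|---|---|---|
| 5 | −6.2 | 4.9 |
| 10 | −11.2 | 59 |
| 15 | −16.2 | 720 |

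There is no limit to report, although the logrank p-value is about 4 × 10⁻⁶. These fits were run in Python, not SAS.

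**Expected cases.** With exponential event times and dropout hazard −ln(0.85)/2 per year, 22 months from Day 60 gives 16.3 control and 4.9 vaccine cases, about 21. A full 34 months gives 24.2 and 7.3, about 31. Subjects enrolled early contribute up to the last subject's Month 24 visit or their own Month 36 visit, so the truth lies between.

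**Chance of zero vaccine cases at VE 70%.** Given D cases in total, a case falls in the vaccine arm with probability 0.3/1.3, so P(0) = (1/1.3)^D. The exact 90% lower limit when there are zero follows Section 16: p_U = 1 − 0.05^(1/D), and the limit is 1 − p_U / [r(1 − p_U)].

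| D | P(0) | Exact lower limit, r = 1 |
|---|---|---|
| 10 | 7.3% | 65.1% |
| 12 | 4.3% | 71.6% |
| 15 | 2.0% | 77.9% |
| 18 | 0.9% | 81.9% |
| 21 | 0.40% | 84.7% |
| 25 | 0.14% | 87.3% |
| 30 | 0.04% | 89.5% |

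At D = 21 the exact limit runs from 83.9% (r = 0.95) to 85.4% (r = 1.05). Because a calendar date triggers the analysis, a Poisson count is the fairer model for the primary: exp(−4.9) is about 0.7%, and exp(−7.3) about 0.07%.

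**Gatekeeping.** At 21 primary cases the Wald rule succeeds with 1 to 6 vaccine cases. If 10 of the 21 are Xpert-positive and none is in the vaccine arm, the other 11 must supply those 1 to 6, which has probability 0.94. The joint chance is 7.3% × 0.94, about 6.8%. With 15 Xpert-positive cases it is 2.0% × 0.79, about 1.5%. These are joint probabilities, not conditional on the primary having been met.

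**Error cost of a fallback.** Under VE 0, P(0) = (1/(1 + r))^D. At 21 cases this is 5 × 10⁻⁷ (r = 1) to 8 × 10⁻⁷ (r = 0.95). At 10 cases it is 0.10 to 0.13 percentage points.

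**The case against.** The strongest reply is that little is missing. The exact interval is pre-specified for every case definition and the logrank p-value will be shown, so no reader of a 0 v 21 result would be misled. That stands: the gap is a linking rule, not a method. A reader might infer that the SAP cannot handle a zero-case arm at all, or that the efficacy result would be lost. Section 16 and 11.4.1 show otherwise.

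A second reply is that the criteria require only a Cox interval, and a profile-likelihood Cox interval stays finite. With equal risk sets its lower limit solves 2D ln(1 + HR) = 2.706, giving about 93% for 0 v 21 and 86% for 0 v 10. This is correct, and it is a legitimate remedy. But 11.4.5 names Wald and nothing else, so that choice would also be made after the fact.

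Third, using the exact interval changes the protocol criterion, because it rests on a rate ratio and not a Cox model. That stands, and the fix has to say so.

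Fourth, the secondary probabilities rest on assumed counts. A reader might take the many single-positive cases in SAP 11.8.1 as proof that the secondary will be small. That section does not say whether the single positive was Xpert or culture, and only culture-only cases drop out. Against 21 to 31 expected primary cases, 10 secondary cases would mean an Xpert share of 32% to 48%.

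**Conclusion.** The gap is real and minor. With zero vaccine-arm cases neither confirmatory criterion can be evaluated by the only interval the SAP names, and nothing gives another interval authority to decide.

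For the primary at VE 70%, the chance is 0.40% given 21 cases or about 0.7% on a Poisson count, and lower with more cases. Further accrual is foreseen: SAP Section 9 has a planning stage "From 21 primary TB cases are accrued until all subjects complete their M24 visit". For the secondary it is about 7% to 1% over an assumed 10 to 18 cases, and slightly lower as a joint event with the primary being met. All these figures assume VE 70%. At 21 cases the chance rises to 2.2% at VE 80% and 13.5% at VE 90%.

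The documents do not support the stronger inference that the primary objective is at material risk under the design assumptions. What is at risk is the formal success call, not the evidence.

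**What to change.** Before the primary analysis is unblinded, add one rule to SAP 11.4.1 or 11.4.5, covering the primary and confirmatory secondary objectives. If the vaccine arm has zero cases and the control arm has at least one, the 90% CI for the success criterion is the conditional exact CI of Section 16. Otherwise the Cox/Wald CI applies. A profile-likelihood Cox CI could be named in its place and would keep the protocol's Cox wording. Choose one of the two in advance.

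If the exact CI is chosen, list it in SAP Section 14 as a change from the Cox-based criterion and justify it in the study report, as protocol 11.11 requires.

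The cost is one rule and, for the exact CI, that entry. No new data or larger sample are needed, and no decision changes when the vaccine arm has one or more cases. The added favourable error under VE 0 is bounded as shown above. Nor does the exact rule guarantee success: with equal follow-up its lower limit exceeds 0% only when there are at least 5 cases in total.

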11.6. Details on case whatever the definition

For the subjects who were identified as a case (whatever the definition), the percentage of cases with specific symptoms will be tabulated (not split by groups)

11.7. Assessment of cases versus baseline characteristics

The descriptive statistics (N, mean, standard deviation, min, Q1, median, Q3, max) of the age of the cases will be displayed without split by group for the triggered primary analysis but by group for the end of study analysis.

The distribution of the cases (n) will be given according to gender and according to country without any split by vaccine group for the triggered primary analysis but by group for the end of study analysis.

11.8. Sensitivity analysis for the case definition 1

11.8.1. Sensitivity excluding single positives

During accrual of cases of active pulmonary TB in study TB-018, an unexpectedly high proportion of primary case definition was found to be positive by only one test out of six (3 real-time PCR and 3 cultures performed on sputa collected on different days)

The observations are hypothesized to correlate with intermittent shedding and low bacterial load in the sputa of early-onset active pulmonary TB. The primary objective of the study was concluded to remain appropriate (i.e. diagnosis confirmed by at least one positive GeneXpert or microbiological confirmation test, so it includes even single-positive result out of the 6 performed). However in view of the high number of single-positive cases, the team concluded that the primary analysis should be complemented by a sensitivity analysis excluding single-positive cases.

VE will be estimated from a Cox proportional hazard regression model (VE=1-hazard ratio) and 90% CIs and Wald p-value will be derived. The sensitivity analysis will be unadjusted and performed in the ATP cohort for efficacy. If needed, further exploratory analysis might be performed.

Kaplan-Meier survival curves for the vaccine and control groups will be presented together with p-values from the logrank test.

11.8.2. Conditional exact method for VE and its CI (instead of the cox regression)

VE will consider the exact inference on the relative risk conditionally to the total number of TB cases (according to each case definition) observed and time at risk.

This method computes an exact confidence interval (CI) around the rate ratio (ratio of the event rates in the vaccinated versus control group) and takes into account the sum of the time at risk of the subjects within each group.

RR is defined as the ratio of the incidence rates of the vaccine group over the placebo group.

VE = 1 – RR. A forest plot will be given representing the VE at each level of each of the covariates (see section 11.4.3) (and their 90% CI) using this conditional exact method. This is really exploratory and requires caution in interpretation due to the low number of cases.

For technical details, see section 16.

